- Hold/Delay = Treatment can be made up as part of this cycle
- Discontinue = Treatment is totally stopped

8.3 TAS-102: This section applies to adverse events associated with TAS-102. For adverse events associated with panitumumab, please refer to Section 8.1 and for regorafenib, please refer to Section 8.2.

NOTE: This drug is standard of care and FDA approved and, therefore, these are suggested but not mandated.

Complete blood cell counts prior to day 1 and on day 15 of each cycle are recommended. A maximum of 3 dose reductions are permitted to a minimum dose of 20 mg/m² twice daily. Do not escalate TAS-102 dose after it has been reduced.

→ → Use the NCI Common Terminology Criteria for Adverse Events (CTCAE) version 5.0* unless otherwise specified ← ←

CTCAE System/Organ/Class (SOC)	ADVERSE EVENT	ACTION**
BASED ON INTERVAL ADVERSE EVENT		
Hematologic	Neutrophil count decreased at cycle start	
	Grade 2-3	Delay treatment until ANC is ≥ 1500/mm ³ , then resume at same dose.
	Grade 4	Delay treatment until ANC is ≥ 1500/mm ³ . If recovery ≤ 1 week, resume at same dose. If recovery > 1 week, resume at 5mg/m ² /dose lower than previous dose.
	Neutrophil count decreased during cycle	
	Grade 4	Withhold treatment until ANC is ≥ 1500/mm ³ . If recovery ≤ 1 week, resume at same dose. If recovery > 1 week, resume at 5mg/m ² /dose lower than previous dose.

→ → Use the NCI Common Terminology Criteria for Adverse Events (CTCAE) version 5.0* unless otherwise specified ← ←

CTCAE System/Organ/Class (SOC)	ADVERSE EVENT	ACTION**
	Febrile neutropenia at cycle start	
	Grade 3	Delay treatment until ANC is $\geq 1500/\text{mm}^3$ and fever is resolved. After recovery, resume at $5\text{mg}/\text{m}^2/\text{dose}$ lower than previous dose.
	Febrile neutropenia during cycle	
	Grade 3	Withhold treatment until ANC is $\geq 1500/\text{mm}^3$ and fever is resolved. After recovery, resume at $5\text{mg}/\text{m}^2/\text{dose}$ lower than previous dose.
	Platelet count decreased at cycle start	
	Grade 2-3	Delay treatment until platelet count is $\geq 75,000/\text{mm}^3$. After recovery, resume at same dose.
	Grade 4	Delay treatment until platelet count is $\geq 75,000/\text{mm}^3$. If recovery ≤ 1 week, resume at same dose. If recovery > 1 week resume at $5\text{mg}/\text{m}^2/\text{dose}$ lower than previous dose.
	Platelet count decreased during cycle	
	Grade 2-3	Withhold treatment until platelet count is $\geq 75,000/\text{mm}^3$. After recovery, resume at same dose.

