	Grade 4	Withhold treatment until platelet count is $\geq 75,000/\text{mm}^3$. If recovery ≤ 1 week, resume at same dose. If recovery > 1 week resume at $5\text{mg}/\text{m}^2/\text{dose}$ lower than previous dose.
General Disorders and administration site conditions	Fatigue	
	Grade 3	Delay until resolved to grade ≤ 1 . Resume at $5\text{mg}/\text{m}^2/\text{dose}$ lower than previous dose.
	Grade 4	Discontinue ^a
Gastrointestinal disorders	Mucositis oral	
	Grade 3	Delay until resolved to grade ≤ 1 . Resume at $5\text{mg}/\text{m}^2/\text{dose}$ lower than previous dose.
	Grade 4	Discontinue ^a

^a For all Grade 3 or 4 AEs except for Grade 3 nausea and/or vomiting controlled by antiemetic therapy or Grade 3 diarrhea responsive to antidiarrheal medication.

* Located at [REDACTED]

** Use the following to describe actions in the Action column:

- Omit = Treatment is not given for this cycle
- Hold/Delay = Treatment can be made up as part of this cycle
- Discontinue = Treatment is totally stopped

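### Footnote a of the TAS-102 table (Section 8.3) attaches a permanent stop to Grade 3 or 4 events that 11 of the table's 13 rows handle by delaying and resuming

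*Combined protocol and SAP*

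**What the plan says.** Section 8.3 gives dose modifications for TAS-102, one of the two control drugs.

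- **The marker.** Footnote a appears twice, as "Discontinue ^a", in the Grade 4 fatigue row and the Grade 4 oral mucositis row.
- **The footnote.** It reads "For all Grade 3 or 4 AEs except for Grade 3 nausea and/or vomiting controlled by antiemetic therapy" and adds an exception for Grade 3 diarrhea that responds to antidiarrheal drugs. It contains no verb.
- **The action it is attached to.** The key below the table defines it: "Discontinue = Treatment is totally stopped".
- **The Grade 3 fatigue and Grade 3 mucositis rows.** These say "Delay until resolved to grade ≤ 1 . Resume at" a dose 5 mg/m² lower.
- **The hematologic rows.** After Grade 2-3 neutropenia at cycle start, the site waits for recovery, "then resume at same dose". After Grade 4 neutropenia, the rule is "If recovery ≤ 1 week, resume at same dose. If recovery > 1 week, resume at" a dose 5 mg/m² lower. The Grade 2-3 platelet rows say "After recovery, resume at same dose".
- **The reduction allowance.** The text above the table permits at most 3 reductions, down to 20 mg/m² twice daily.
- **Status.** A note at the start of Section 8.3 says that the modifications are suggestions and not mandatory. Section 7.12 leaves control dosing to prescribing guidelines and the investigator. Section 8.0 lets the investigator depart from the listed modifications for the subject's safety.

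**The concern.** A footnote without a verb takes its action from the word that it marks. Here that word is a permanent stop, and the footnote applies it to nearly all Grade 3 or 4 events. The rows beside it tell the site to delay or withhold and then resume after many of the same events. One site could act on the rows and another on the footnote, each able to cite Section 8.3.

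The choice has consequences for the data. Section 7.12 bars switching between TAS-102 and regorafenib during protocol treatment, so stopping TAS-102 ends protocol treatment for that patient. Under Section 13.3 the patient then enters event monitoring every 3 months, whereas Section 11.1 sets re-evaluation every 8 weeks. Different readings could therefore change time on treatment and the timing of follow-up in the control arm. That touches progression-free survival, adverse events and quality of life and, through exposure, possibly overall survival.

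**Working it through.** The check sets the footnote against every action row. The only arithmetic is a count of rows and the dose ladder.

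**The plan's own figure.** Section 7.1 starts TAS-102 at 35 mg/m². The reduction rows in Section 8.3 step down by 5 mg/m², with at most 3 steps: 35 − 3 × 5 = 20 mg/m². This reproduces the stated minimum, so the ladder and the reduction rows agree with each other.

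**The rows.**

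| # | Event in the Section 8.3 table | Grade | Action | Reduction possible? | Agrees with the footnote read as a stop? |
|---|---|---|---|---|---|
| 1 | Neutrophils, cycle start | 2-3 | Delay, resume | No | No, for Grade 3 |
| 2 | Neutrophils, cycle start | 4 | Delay, resume | Yes | No |
| 3 | Neutrophils, during cycle | 4 | Withhold, resume | Yes | No |
| 4 | Febrile neutropenia, cycle start | 3 | Delay, resume | Yes | No |
| 5 | Febrile neutropenia, during cycle | 3 | Withhold, resume | Yes | No |
| 6 | Platelets, cycle start | 2-3 | Delay, resume | No | No, for Grade 3 |
| 7 | Platelets, cycle start | 4 | Delay, resume | Yes | No |
| 8 | Platelets, during cycle | 2-3 | Withhold, resume | No | No, for Grade 3 |
| 9 | Platelets, during cycle | 4 | Withhold, resume | Yes | No |
| 10 | Fatigue | 3 | Delay, resume | Yes | No |
| 11 | Fatigue | 4 | Stop (marker a) | – | Yes |
| 12 | Oral mucositis | 3 | Delay, resume | Yes | No |
| 13 | Oral mucositis | 4 | Stop (marker a) | – | Yes |

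**Counts.**

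- Rows in conflict: 3 neutrophil + 2 febrile neutropenia + 4 platelet + 1 fatigue + 1 mucositis = 11 of 13. Only the 2 rows that carry the marker agree.
- Rows that can reduce the dose: numbers 2, 3, 4, 5, 7, 9, 10 and 12, which makes 8. Each is triggered by a Grade 3 or 4 event, and none is among the footnote's exceptions. If the footnote meant a stop for all such events, no row could produce a reduction, and the ladder from 35 to 20 mg/m² could never be reached through the table.

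**Events with no row.** The footnote's exceptions concern nausea, vomiting and diarrhea. None has a row in the TAS-102 table, although Section 15.37 lists all three among the toxicities seen in at least 10% of patients. Section 9 covers their supportive care but gives no TAS-102 dose action. The footnote is therefore the only dose text in Section 8.3 that names them, and it does not state the action.

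**Could the marker's position settle it?** A note meant only for Grade 4 fatigue and Grade 4 mucositis would have no reason to mention Grade 3, nausea, vomiting or diarrhea. The position of the marker and the content of the note point to different scopes.

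**The case against.** The strongest reply is that Section 8.3 binds no one. Its modifications are suggestions, and Sections 7.12 and 8.0 give the investigator discretion. Some variation in TAS-102 handling between sites is already permitted and would remain after the footnote was repaired. This stands, and it limits the consequence. It does not excuse guidance that points two ways on the same event.

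The second reply is that few sites would act on the literal reading. It would void most of the table, so a site might well see a misplaced or truncated note. The footnote may have been meant for events with no row of their own, since its exceptions are all such events. On that reading the conflict with the neutrophil, platelet, fatigue and mucositis rows disappears. This is plausible but nothing in the documents says it, and the action for the unlisted events would still be uncertain.

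A reader might also infer more than the text allows: that TAS-102 would be stopped too early, that control survival would suffer, and that the primary comparison would tilt towards panitumumab. The documents do not support this, for four reasons.

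- Calling a stop too early assumes that the delay-and-resume rows are the intended rule. The documents do not say which text governs.
- Only control patients given TAS-102 are affected. Regorafenib has its own table in Section 8.2, and no expected split between the two drugs is given.
- Section 16.11 measures overall survival from randomization to death from any cause. Under Section 13.3, patients who go off treatment are still followed for survival, and later therapy is at the physician's discretion. Stopping TAS-102 therefore neither censors survival nor ends treatment options.
- No event rates are given from which an effect through reduced exposure could be sized, and its net direction cannot be established.

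**Conclusion.** The contradiction is real and lies within a single table. Footnote a, read with the action it marks, opposes 11 of 13 rows and makes the 3-step reduction allowance unreachable through that table. It also leaves the action unclear for Grade 3 or 4 events that have no row. The footnote, its markers and the rows are all legible, and no other section resolves the conflict.

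This rests on one assumption, that a footnote without a verb modifies the word it is attached to. If it was misplaced or has lost words, it still needs correcting.

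The supportable consequence is inconsistent handling of TAS-102 between sites, within guidance that is advisory. A claim of bias in the primary comparison does not follow. The point is an internal inconsistency in site-facing text, worth correcting, and it does not call the sample size, the power or the decision rules into question.

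**What to change.** Reconcile footnote a with the Section 8.3 rows. The revised footnote should state three things:

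- which events it covers, and in particular whether it applies to events that have their own row or only to those without one;
- which grades it covers;
- which action it modifies, in words, so that the meaning does not depend on where the marker sits.

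The result should then be checked against the allowance of up to 3 reductions above the table. Which clinical rule applies is for the sponsor to decide, and no rule is proposed here.

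The cost is one line of footnote wording, with the marker moved if needed. No change to the design, sample size or analysis follows from it.

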9.0 Ancillary Treatment/Supportive Care

- 9.1 Antiemetics may be used at the discretion of the attending physician.
- 9.2 Blood products and growth factors should be utilized as clinically warranted and following institutional policies and recommendations. The use of growth factors should follow published guidelines of the American Society of Clinical Oncology

(ASCO) Recommendations for the Use of WBC Growth Factors: American Society of Clinical Oncology Clinical Practice Guideline Update. *J Clin Oncol* 2015; 33:3199-3212.

9.3 Patients should receive full supportive care while on this study. This includes blood product support, antibiotic treatment, and treatment of other newly diagnosed or concurrent medical conditions. All blood products and concomitant medications such as antidiarrheals, analgesics, and/or antiemetics received from the first day of study treatment administration until 30 days after the final dose will be recorded in the medical records.

9.4 Diarrhea: This could be managed conservatively with loperamide. The recommended dose of loperamide is 4 mg at first onset, followed by 2 mg every 2-4 hours until diarrhea free (maximum 16 mg/day).

In the event of grade 3 or 4 diarrhea, the following supportive measures are allowed: hydration, octreotide, and antidiarrheals.

If diarrhea is severe (requiring intravenous rehydration) and/or associated with fever or severe neutropenia (grade 3 or 4), broad-spectrum antibiotics must be prescribed. Patients with severe diarrhea or any diarrhea associated with severe nausea or vomiting **should be hospitalized** for intravenous hydration and correction of electrolyte imbalances.

9.5 Management of regorafenib-related Adverse Events

At first occurrence of palmar-planter erythrodysesthesia syndrome (PPES), independent of grade, prompt institution of supportive measures such as topical emollients, low potency steroids, or urea-containing creams should be administered.

9.51 Recommended prevention/management strategies for skin toxicities consistent with PPES are summarized below:

Control of calluses

Before initiating treatment with regorafenib:

- Check condition of hands and feet.
- Suggest a manicure/pedicure, when indicated.
- Recommend pumice stone use for callus or 'rough spot' removal.

During regorafenib treatment:

- Avoid pressure points.
- Avoid items that rub, pinch or create friction.

Use of creams

- Over the counter moisturizing creams or ointments are allowed

- For grades 2 or 3, topical analgesics (e.g. lidocaine 5% patches, lidocaine/prilocaine cream TID, lidocaine 2-5% creams) are to be considered for pain control.
- Topical corticosteroids like clobetasol 0.05% should be instituted for subjects with Grade 2 or 3 PPES.
- For grade 2/3 Oral NSAIDs (celecoxib, ibuprofen) may be used for pain control

Tender areas should be protected as follows:

- Use of thick socks/gloves to cover moisturizing creams
- Wear well-padded footwear
- Use insole cushions or inserts (e.g. silicon, gel)
- Foot soaks with tepid or cool water
- Use soft shoes or slippers (Crocs, TempurPedic slippers), avoid high heels and wood soles/heels

Suggested PPES Reaction Treatment

- CTCAE v5 Grade 1 ((Minimal skin changes or dermatitis (e.g., erythema, edema or hyperkeratosis) without pain)) - Continue regorafenib at current dose.
- CTCAE v5 Grade 2 ((Skin changes (e.g., peeling, blisters, bleeding, edema, or hyperkeratosis) with pain, limiting instrumental ADL (or intolerable grade 2, defined as grade 2 AE that does not decrease to grade ≤ 1 after 2 weeks of therapy OR that is considered intolerable per patient))
 - Oral (NSAIDs or narcotics) OR topical analgesia (lidocaine cream or patches PRN.
- CTCAE v5 Grade ≥ 3 ((Ulcerative dermatitis or skin changes with pain interfering with function. Severe skin changes (eg, peeling, blisters, bleeding, edema, or hyperkeratosis) with pain; limiting self-care ADL))
 - Topical steroid cream BID AND topical anesthetics
 - Oral (NSAIDs or narcotics) OR topical analgesia (lidocaine cream or patches PRN.

9.6 Hypomagnesemia: Panitumumab should be held for severe and/or life threatening hypomagnesemia. Consider IV replacement and magnesium oxide 400 mg PO BID.

9.7 Panitumumab-related skin rash. The treating physician may elect to preemptively treat subjects receiving panitumumab to mitigate or prevent skin toxicities. Doxycycline 100mg every 12 hours or equivalent, emollient, and hydrocortisone 1% cream is recommended, but not required for skin rash prophylaxis (Refer to Section 8.1)

9.8 Hypertension: Early and aggressive medical management of hypertension is strongly recommended to minimize the need for dose holding and/or dose reductions. Addition or adjustment of blood pressure medications should be considered for blood pressure values persistently $> 140/90$. Symptomatic or asymptomatic patients with poorly controlled blood pressure ($> 150/100$ on 3 measurements over 2 weeks) for over one month (despite the addition and

adjustment of anti-hypertensive therapy) should have regorafenib held until their blood pressure is $\leq 140/90$.

9.9 Prohibited Concomitant Therapy

The following therapies are prohibited during the study (unless otherwise noted):

- Investigational drugs and devices
- Anti-cancer therapy, including but not limited to chemotherapy and hormonal therapy
- Radiation therapy, except for palliative radiotherapy at focal non-CNS sites which are not considered target lesions per RECIST 1.1, which may be given after consultation with the medical monitor, provided that there remain other sites of assessable disease accessible by RECIST 1.1
- Strong inhibitors or inducers of CYP3A4. Known strong inhibitors of CYP3A4 include, but are not limited to, ketoconazole, itraconazole, clarithromycin, erythromycin, atazanavir, indinavir, nefazodone, neflifavir, ritonavir, saquinavir, telithromycin, and voriconazole. Known inducers of CYP3A4 include, but are not limited to phenytoin, carbamazepine, barbiturates, and St. John's Wort. Partial and more complete lists of strong inhibitors and inducers may be found in other reference material.
- Caution is required when using drugs that are human thymidine kinase substrates, e.g., zidovudine.

10.0 Adverse Event (AE) Reporting and Monitoring

The site principal investigator is responsible for reporting any/all adverse events to the sponsor as described within the protocol. Refer to the adverse event and serious adverse event sections of the protocol for detailed information.

NOTE: Please see Appendix V for specific AE reporting regarding the study drug panitumumab for ACCRU personnel only.

ACCRU is responsible for notifying FDA and all participating investigators in a written safety report of any of the following:

- Any suspected adverse reaction that is both serious and unexpected.
- Any findings from laboratory animal or *in vitro* testing that suggest a significant risk for human subjects, including reports of mutagenicity, teratogenicity, or carcinogenicity.
- Any findings from epidemiological studies, pooled analysis of multiple studies, or clinical studies, whether or not conducted under an IND and whether or not conducted by the sponsor, that suggest a significant risk in humans exposed to the drug.
- Any clinically important increase in the rate of a serious suspected adverse reaction over the rate stated in the protocol or Investigator's Brochure (IB).

Definitions

Adverse Event

Any untoward medical occurrence associated with the use of a drug in humans, whether or not considered drug related.

The investigator is responsible for ensuring that all adverse events observed by the investigator or reported by the subject that occur after the first dose of investigational product(s)/study treatment through the safety follow-up visit are reported using the Event CRF.

Events Meeting the Adverse Event Definition

- Any abnormal laboratory test results (hematology, clinical chemistry, or urinalysis) or other safety assessments (eg, electrocardiogram, radiological scans, vital signs measurements), including those that worsen from baseline, that are considered clinically significant in the medical and scientific judgment of the investigator (ie, not related to progression of underlying disease).
- Exacerbation of a chronic or intermittent pre-existing condition including either an increase in frequency and/or intensity of the condition.
- New conditions detected or diagnosed after study treatment administration even though it may have been present before the start of the study.
- Signs, symptoms, or the clinical sequelae of a suspected drug-drug interaction.

Definition of Serious Adverse Event

A Serious Adverse Event is defined as any untoward medical occurrence that, meets at least 1 of the following serious criteria:

Results in death (fatal)**Immediately life-threatening**

The term “life-threatening” in the definition of “serious” refers to an event in which the subject was at risk of death at the time of the event. It does not refer to an event, which hypothetically might have caused death, if it were more severe.

Requires in-patient hospitalization or prolongation of existing hospitalization

In general, hospitalization signifies that the subject has been detained (usually involving at least an overnight stay) at the hospital or emergency ward for observation and/or treatment that would not have been appropriate in the physician’s office or outpatient setting. Complications that occur during hospitalization are an adverse event. If a complication prolongs hospitalization or fulfills any other serious criteria, the event is serious. When in doubt as to whether “hospitalization” occurred or was necessary, the adverse event is to be considered serious. Hospitalization for elective treatment of a pre-existing condition that did not worsen from baseline is not considered an adverse event.

Results in persistent or significant disability/incapacity

The term disability means a substantial disruption of a person’s ability to conduct normal life functions. This definition is not intended to include experiences of relatively minor medical significance such as uncomplicated headache, nausea, vomiting, diarrhea, influenza, and accidental trauma (eg, sprained ankle) which may interfere with or prevent everyday life functions but do not constitute a substantial disruption.

Is a congenital anomaly/birth defect**Other medically important serious event**

Medical or scientific judgment is to be exercised in deciding whether serious adverse event reporting is appropriate in other situations such as important medical events that may not be immediately life-threatening or result in death or hospitalization but may jeopardize the subject or may require medical or surgical intervention to prevent 1 of the other outcomes listed in the above definition. These events are typically to be considered serious.

Suspected Adverse Reaction

Any adverse event for which there is a reasonable possibility that the drug caused the adverse event.

Expedited Reporting

Events reported to sponsor within 24 hours, 5 days or 10 days of study team becoming aware of the event. All SAEs that occur after the subject has signed the main informed consent through the safety follow-up visit or 30 days after the last dose of protocol-specified therapy, whichever is later, will be reported to Amgen and recorded in the case report form. SAEs must be reported to Amgen within 24 hours of discovery.

Routine Reporting

Events reported to sponsor via case report forms

Events of Interest

Events that would not typically be considered to meet the criteria for expedited reporting, but that for a specific protocol are being reported via expedited means in order to facilitate the review of safety data (may be requested by the FDA or the sponsor).

Events NOT Meeting the Adverse Event Definition

Medical or surgical procedure (eg, endoscopy, appendectomy): the condition that leads to the procedure is the adverse event.

Situations in which an untoward medical occurrence did not occur (social and/or convenience admission to a hospital).

Anticipated day-to-day fluctuations of pre-existing disease(s) or condition(s) present or detected at the start of the study that do not worsen.

